Official title: Persistent Lymphopenia in Liver Transplantation and Its Molecular Insights for Hepatocellular Carcinoma

NCT number:

Document date: 2021/10/20

Study Protocol and Statistical Analysis Plan:

The subjects of this study were HCC patients with low lymphocytes (experimental group) and normal lymphocytes (control group). The sample type was blood and was divided into two parts: retrospective and prospective.

The source of retrospective blood (including serum, plasma or white blood cells) is to apply for specimens from tissue banks and biobank of Kaohsiung Chang Gung Memorial Hospital (KCGMH). At the same time, the patient's medical record, such as gender, age, lymph node, etc. will also be requested. The number of cells, total number of white blood cells, survival, recurrence, biochemical test data and other information are collected.

Prospective blood is newly collected. The source is that during the patient's treatment, about 20ml blood is drawn during routine examinations. This will not increase the burden on the patient. We will ask the patient one week before collecting the specimen if he is willing to provide the specimen for research purposes, and we guarantee that his personal information and privacy will not be disclosed. Unused specimens will be destroyed after the research is completed.

We will perform retrospective analysis at first. 145 HCC patients will be divided into 2 groups with or without lymphopenia, followed by comparing the effects of clinical data between them. Blood samples will be collected to analyze the impact and expression of protein, gene and microRNA (miRNA). Next Generation Sequencing (NGS) will be applied to find unknown important factors. In prospective study, 20 lymphopenia and 25 non-lymphopenia HCC recipients were enrolled, and a phenotypic analysis of peripheral blood lymphocytes was performed using multiparameter flow cytometry to identify the major immune cell subsets and validate previous results.

One-way analysis of variance will be used with Bonferroni's post hoc analysis for comparison between multiple groups. Student's t test will be used for comparison of continuous data between two groups while chi-square for discrete data. Significance is defined as $P < 0.05$.

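### Chi-square is the only test for discrete data and there is no sparse-table rule; if lymphopenia is uncommon (for example 29 of 145), one patient v none gives P=0.045 (exact 0.20)

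*Combined protocol and SAP*

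**What the plan says.** The statistical methods are the final paragraph of the combined protocol and SAP. For two-group comparisons it says: "Student's t test will be used for comparison of continuous data between two groups while chi-square for discrete data", with significance at P below 0.05. It does not name an exact test, set an expected-count threshold or say whether a continuity correction is applied.

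On the groups, the retrospective paragraph says "145 HCC patients will be divided into 2 groups with or without lymphopenia". It does not give the number in each group. For the prospective part, "20 lymphopenia and 25 non-lymphopenia HCC recipients were enrolled".

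On the variables, "the patient's medical record, such as gender, age, lymph node, etc. will also be requested", and the same paragraph adds outcome and laboratory items. No frequency is given for any discrete feature.

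**The concern.** The chi-square P-value is a large-sample approximation. It is least reliable when a feature is rare and the two groups differ much in size, because the expected count in the smaller group can then fall well below 1. The retrospective groups are formed by an observed characteristic, so their sizes are not under design control, and the plan does not exclude a very uneven split.

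At stake is a clinical difference reported as significant on the strength of a single patient. The result would also depend on whether the software applies a continuity correction by default, which the plan leaves open.

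**Working it through.** **Inputs.** From the plan: chi-square for discrete data, significance at P<0.05, N=145 in the retrospective part, 20 v 25 in the prospective part. Assumed, because the plan is silent: the split of the 145 (varied), the prevalence of a rare feature (varied), and the uncorrected Pearson statistic. The plan has no figure of its own on this point to reproduce.

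**Formula.** Suppose k patients have a feature and all are in the smaller group of n1, with n2 in the other group and N = n1 + n2. Then

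- Pearson chi-square = N·k·n2 / [n1·(N − k)], on 1 degree of freedom (critical value 3.84);
- two-sided Fisher P = [n1(n1 − 1)…(n1 − k + 1)] / [N(N − 1)…(N − k + 1)] for the three tables below, where every other table with the same margins is more probable;
- smallest expected count = k·n1/N.

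**Single tables.**

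| Table | Chi-square | P | Exact P | Smallest expected count |
|---|---|---|---|---|
| 1 v 0 at 29/116 | 145×1×116/(29×144) = 4.03 | 0.045 | 29/145 = 0.20 | 0.20 |
| 2 v 0 at 45/100 | 145×2×100/(45×143) = 4.51 | 0.034 | (45×44)/(145×144) = 0.095 | 0.62 |
| 3 v 0 at 20/25 | 45×3×25/(20×42) = 4.02 | 0.045 | (20×19×18)/(45×44×43) = 0.080 | 1.33 |

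**How far this reaches.** For 1 v 0, chi-square is 145×115/(30×144) = 3.86 at 30/115 (P=0.0495) and 145×114/(31×144) = 3.70 at 31/114 (P=0.054). One patient is therefore enough only if that patient is in the smaller group and the group has 30 or fewer. For 2 v 0 the limit is 50. Scaling 20:25 to 145 gives about 64:81, where 1 v 0 gives P=0.26 and 2 v 0 gives 0.11; three patients are then needed (0.049, exact 0.084). At 72:73 it takes four (0.041, exact 0.058).

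**True type I error.** One discordant table does not show that the test is too liberal overall. For that, all 2×2 tables were enumerated with the same true prevalence in both groups, over prevalences from 0.5% to 99.5%, using uncorrected chi-square at 0.05:

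| Split | Size at 1% | Size at 2% | Maximum size |
|---|---|---|---|
| 29/116 | 9.2% | 7.5% | 9.2% |
| 20/125 | 6.2% | 5.7% | 6.2% |
| 45/100 | 2.8% | 3.5% | about 5.2% |
| 64/81 | 1.3% | 3.6% | 5.6% |
| 72/73 | 0.6% | 2.7% | 5.2% |
| 20/25 | 0.1% | 0.4% | 5.2% |

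At 29/116 the size is 3.6% at 5% prevalence and 4.6% at 10%, so the excess is confined to rare features.

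**Where the 9.2% comes from.** At 1% prevalence the table 1 v 0 has probability 29 × 0.01 × 0.99^144 = 0.29 × 0.235 = 0.068. Most of the error rate is this one table.

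**Continuity correction.** With Yates' correction, 1 v 0 at 29/116 gives P=0.45 and 2 v 0 at 45/100 gives P=0.18.

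**The case against.** The strongest reply is that the problem depends on things the plan does not say. The split is unknown, and the only group sizes given (20 v 25) suggest a fairly even one. At such splits chi-square keeps its error rate near or below 5%, and one or two patients cannot reach significance. Fisher's test is itself conservative, so a chi-square P below the Fisher P is not proof of error. This stands, and it limits the point to a small smaller group combined with a rare feature. It does not remove it, because nothing in the plan excludes that case.

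The continuity-correction argument also stands: an analyst using Yates' correction would not see the 1 v 0 or 2 v 0 results tabulated above. But the plan does not say which version applies, which is itself a reason to state it.

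A reader might infer three stronger things that the documents do not support:

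- **That one or two patients will give false significance in this study, with exact P between 0.09 and 0.20.** Those values belong to two assumed tables. Over all splits of 145, where chi-square is significant and Fisher is not, the exact P for one or two patients runs from about 0.05 to 0.21. If the smaller group exceeds 50, neither one nor two patients is enough.
- **That the molecular screening is compromised.** Protein, gene and miRNA expression and the flow-cytometry subsets are naturally continuous. The plan states no rare molecular category and no significance threshold other than 0.05.
- **That using chi-square for ordered categories is an error.** It is valid there, though possibly less powerful than a trend test. The plan names no graded variable on which to judge the loss.

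**Conclusion.** The point holds as a conditional one. The plan prescribes an approximate test for all discrete data with no provision for sparse tables, and leaves open both the split of the 145 and the version of the statistic. If the smaller group has 30 or fewer patients and the uncorrected statistic is used, a single patient can produce a significant result. The size of the inflation varies within that range: up to 9.2% at 29/116 but 6.2% at 20/125, in both cases for features of about 1% prevalence. At the other splits examined, including the stated 20/25, discordant tables occur but the overall error rate is at most about 5.6%.

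This is a cheap improvement worth making, not evidence that the planned comparisons are generally invalid.

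**What to change.** Add one sentence to the statistical paragraph, for example:

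> Chi-square without continuity correction is used when every expected count is at least 1; otherwise Fisher's exact test is used.

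The mid-P version of the exact test is a reasonable alternative, but the SAP should name one of the two, because they can differ. Mid-P halves the probability of the observed table, so 1 v 0 at 29/116 becomes 0.20/2 = 0.10, while 2 v 0 at 45/100 becomes 0.095/2 = 0.047, still below 0.05.

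**Effect.** With Fisher as the fallback, size at 29/116 and 1% prevalence falls from 9.2% to 1.2%. The maximum over all prevalences falls from 9.2% to 5.1% at 29/116 and from 6.2% to 5.2% at 20/125. The rule leaves 3 v 0 at 20/25 on chi-square, because its smallest expected count is 1.33. That is acceptable, since the error rate at that split is already controlled.

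**Cost.** One sentence and no new data. Exact tests are somewhat conservative in sparse tables, as the 1.2% shows, so a little power is given up for rare features. Stating the number with and without lymphopenia among the 145, once known, would show whether the issue arises at all. A trend test for ordered categories is optional and separate from this point.

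### A single P < 0.05 rule governs an open NGS, gene, miRNA and protein screen with no error control across features, so the number of false molecular hits is uncontrolled

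*Combined protocol and SAP*

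**What the plan says.** The document is a combined protocol and SAP under one heading. The paragraph on the retrospective analysis sets up the main contrast: "145 HCC patients will be divided into 2 groups with or without lymphopenia". It then describes the molecular work: "Blood samples will be collected to analyze the impact and expression of protein, gene and microRNA (miRNA)" and "Next Generation Sequencing (NGS) will be applied to find unknown important factors". The same paragraph adds a prospective set of 20 patients with and 25 without lymphopenia, studied by "multiparameter flow cytometry to identify the major immune cell subsets and validate previous results".

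The final paragraph is the whole statistical plan, in three sentences. The first is "One-way analysis of variance will be used with Bonferroni's post hoc analysis for comparison between multiple groups". The second is "Student's t test will be used for comparison of continuous data between two groups while chi-square for discrete data". The third sets the threshold: "Significance is defined as $P < 0.05".

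The document states no false discovery rate, no family-wise control across features, no separate rule for NGS, no candidate list, no number of features per assay, and no exploratory label for the molecular results.

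**The concern.** A search for unknown factors tests many features, and a per-test threshold of 0.05 does not limit how many null features pass. The title promises molecular insights, and those depend on the NGS, gene, miRNA and protein analyses together. Under the rule as written, the resulting list has no stated error rate, and a reader could not tell how many of its entries to expect by chance.

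The Bonferroni sentence might seem to cover this, but it works in a different direction. It corrects for the number of group pairs within one variable, not for the number of variables. Two groups form only one pair, and the plan sends two-group comparisons to tests that carry no adjustment.

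**Working it through.** The plan has no power, sample-size or error-rate calculation to reproduce. Its usable inputs are the threshold of 0.05, the total of 145 patients and the two-group contrast. The feature count, share of true differences, power, group split and number of patients assayed are not given, so each value below is an assumption.

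**1. Reach of the Bonferroni step.** Two groups give 1 pair, so the threshold stays at 0.05. Three groups would give 3 pairs and 0.05/3 = 0.0167 each. In neither case does the number of features enter.

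**2. Expected false hits if no feature differs.** Expected count = m × 0.05, where m is the number of features.

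| m (assumed) | Expected false hits |
|---|---|
| 100 | 5 |
| 500 | 25 |
| 1,000 | 50 |
| 20,000 | 1,000 |

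For m = 1,000 with independent features, the 95% range is 37 to 64. A simulation of 200 null screens averaged 49.6. Correlation between features leaves the expected count unchanged but widens the spread.

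**3. False share of declared hits.** With π the share of features that truly differ, the false share is (1−π) × 0.05 / [(1−π) × 0.05 + π × power]. At 80% power:

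- π = 1%: 0.0495 / (0.0495 + 0.008) = 86%
- π = 5%: 0.0475 / (0.0475 + 0.040) = 54%
- π = 10%: 0.045 / (0.045 + 0.080) = 36%
- π = 20%: 0.040 / (0.040 + 0.160) = 20%

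The share equals one half at π = 0.05 / (0.05 + 0.80) = 5.9%. Most hits are false only when fewer features than that truly differ.

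**4. Unadjusted P < 0.05 against Benjamini-Hochberg at 5%.** Simulation of 2,000 runs with 1,000 independent features, 50 of them truly different, two-sided t tests and all 145 patients assayed. The table gives mean counts; d is the standardised difference.

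| Split | d | P < 0.05: false / true | BH 5%: false / true | Realised FDR under BH |
|---|---|---|---|---|
| 72/73 | 0.5 | 47.6 / 42.4 | 0.98 / 18.3 | 0.048 |
| 72/73 | 0.8 | 47.4 / 49.9 | 2.4 / 47.8 | 0.047 |
| 45/100 | 0.5 | 47.6 / 39.5 | 0.7 / 12.7 | 0.047 |

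**5. Only a subset sequenced.** With an assumed 10 versus 10 patients and d = 0.8, P < 0.05 gives about 48 false and 20 true hits, so 48/68, or about 70%, are false. Benjamini-Hochberg keeps about 0.3 true hits. At d = 0.5 the true hits are about 9 unadjusted and 0.05 adjusted.

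**6. Flow cytometry.** For an assumed 20 null cell subsets, 20 × 0.05 = 1 false hit is expected. The chance of at least one is 1 − 0.95^20 = 64% if the subsets are independent. The problem here is the same in kind and much smaller.

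**The case against.** *The plan does not tie P < 0.05 to NGS.* No test is linked to the sequencing output, which might serve only to nominate candidates. That is true. But P < 0.05 is the only decision rule in the document and it is unqualified, so an analyst following the text would apply it.

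*The size is not the trial's own.* The 1,000 features are a scaling unit. Only the NGS step is described as a search for unknowns, and the protein, gene and miRNA assays could be small panels: 10 candidates would give 10 × 0.05 = 0.5 expected false hits. This limits the size for such panels. It does not limit it for the open search, and the plan states no panel size.

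*The design is staged.* Discovery followed by independent validation is a recognised safeguard. If every one of 1,000 null features were retested at 0.05, about 1,000 × 0.05 × 0.05 = 2.5 would pass both stages, or 1.25 in the same direction. The plan does not provide for that. The prospective assay it describes measures lymphocyte subsets, and there is no replication rule for molecular features.

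*The remedy costs power.* This stands, and it is severe if few patients are sequenced, as step 5 shows. The unadjusted list in that case is also about 70% false, so leaving the rule as it is does not rescue it.

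*The work is exploratory, with no treatment decision resting on a hit.* That is a reason to choose false discovery rate control with an exploratory tier over strict family-wise control. The plan applies no such label itself.

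**Conclusion.** The concern holds and should be fixed. The absence of control across features is clear from the text and depends on no assumption. Its size does: it varies with the unstated number of features, share of true differences, effect sizes and number of patients assayed. It ranges from negligible for a panel of about ten candidates to hundreds of false hits or more for a screen of many thousands of features. Confidence in the size is moderate for that reason. The clinical comparisons are not affected by this point.

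**What to change.** In the statistical paragraph:

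- Keep P < 0.05 for the clinical comparisons.
- For each molecular assay family (NGS, gene, miRNA, protein) and for the flow cytometry subsets, report the number of features tested and declare hits by Benjamini-Hochberg at a 5% false discovery rate within the family.
- Label features that pass only the unadjusted threshold as exploratory.
- State that the prospective flow cytometry validates only the features it measures.

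This needs wording and standard software, with no new patients or assays. It gives up some modest true effects as declared hits, though the exploratory tier keeps them visible. The loss depends on how many patients are assayed, so the plan should state that number as well.
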